Based on the special disease management of Crohn's disease diet studies

——a multicenter, randomized, controlled and open label study

Research Program

(English edition 2.2-August 01, 2021)

**IBD Center, Second Affiliated Hospital of Zhejiang University
School of Medicine**

[name], [name] and [name]

1. Research background

Crohn's Disease (CD) is a chronic, segmental, full-thickness inflammatory bowel disease that involves the whole digestive tract, and is a type of inflammatory bowel Disease (IBD). Its clinical manifestations include diarrhea, hematochezia, abdominal pain and complications such as perforation, fistula formation and even cancer, which greatly affect the quality of life of patients^[1]. CD patients need lifelong treatment and management, so the direct and indirect economic burden has become an unavoidable challenge for all countries in the world.

The pathogenesis of CD is unclear, which may be caused by environmental, genetic, infectious and immune factors^[2]. Studies have shown the incidence of CD in Asia has increased since the 21st century. Considering the huge population base in China, it is predicted that the total number of IBD patients in China is likely to surpass that in North America in the near future^[3]. In the studies related to environmental factors and CD, it has been found that farm life, exposure to animals in childhood^[4], use of antibiotics in childhood^[5] and other factors are related to the incidence of CD. **The reason may be that westernized diet and environment change intestinal flora, thus increasing the incidence of disease in susceptible population^[6].**

Enteral nutrition plays an important role in the treatment of CD, which can not only reduce surgical complications but also improve patients' quality of life with a low incidence of side effects. Exclusive Enteral Nutrition (EEN) is the only established dietary treatment for children with CD. EEN has received particular attention in Europe, where 80% of patients have achieved clinical remission and even intestinal mucosal healing^[7-9]。 Previous studies by our team at the IBD Center showed that EEN induced remission rate in adult patients with CD reached 67%^[10], However, the mechanism of action of EEN in treating IBD remains unclear^[11-13]. So what effect does EEN have on the gut microbiota? Studies indicated that after EEN treatment, the levels of *Bacteroides* and *Firmicutes* in CD patients decreased, while the levels of *Gammaproteobacteria* and *Actinobacteria* and mucosa associated adhesive *Escherichia Coli* increased^[14-17]. The number of anti-inflammatory *Faecalibacterium prausnitzii* has also decreased^[18], In addition, tailed phage viruses^[19] were also increased^[20]. **Changes in diet affect the amount of short-chain fatty acids and branched-chain fatty acids produced by changing the composition of intestinal flora, leading to changes in intestinal state.**

As CD is an incurable lifelong disease, how to maintain disease remission is an extremely important

part of disease management. Although EEN has a good effect on CD induced remission, due to the long treatment cycle and strict condition control, patients cannot eat other food except fixed nutrient solution, which leads to low compliance of patients, especially adults^[10]. Therefore, the promotion of EEN in clinical work is limited, and it is difficult for EEN to be used as the preferred method of CD maintenance treatment.

How to develop a safe, effective and inexpensive treatment for CD patients in China is of great clinical and scientific significance. In recent years, a large number of adjuvant therapies related to CD diet have emerged, such as specific carbohydrate diet therapy^[21] , Low Fodmap diet^[22] , allergen-free diet^[23], etc. But there has been no consistent or convincing evidence on the efficacy of these diets. In 2019, an important study published in the journal Gastroenterology offered a promising diet. The prospective use of half-dose enteral nutrition in combination with a diet-based personalized nutrition regimen (CD-Treat) showed favorable outcomes and high patient compliance in patients with CD^[24]. But the diet in the study was Western-style, and it was a small sample research. Through the long-term clinical observation of our team, most patients with CD can achieve stable remission by removing the processed food and screening the corresponding food by combining the characteristics of Chinese diet with the food intolerance detection method. So, what kind of diet is suitable for the treatment of CD patients in China? We refer to the CD-Treat program, replacing the Western diet with Chinese diet, so as to design an individualized program CD-Chinese-food (CD-C-food) that is consistent with the eating habits of Chinese patients with CD. By comparing the effects of this individualized diet with EEN on inducing and maintaining remission in CD patients. In addition, we used intestinal microbiome, bacterial metabolites, intestinal metabolomics, inflammatory factors and other technical means to deeply analyze the therapeutic mechanism of this new diet regimen for CD patients.

To sum up, this project plans to develop a new diet therapy suitable for China -- CD-C-food. Based on the nutritional analysis of EEN, CD-C-Food is more in line with the common diet of Chinese patients' eating habits and economic conditions, and its expected therapeutic effect and influence on intestinal microorganism are similar to that of EEN. We will conduct a randomized control of adult subjects with a healthy CD-Chinese-food diet, treatment group of CD patients and animal model, using intestinal microbiome, intestinal metabolomics, bacterial metabolite analysis, inflammatory factors detection and other technical means. To explore the influence of intestinal microorganisms and their metabolites on the clinical remission effect and inflammatory response of patients with CD-C-Food CD, and to reveal the

possible internal mechanism; This study lays a foundation for further verification of larger samples in multi-centers across the country, and provides a new approach for the development of CD diet therapy with similar efficacy as EEN, but better taste and higher patient compliance.

References:

3. Chi KR. Epidemiology: Rising in the East. *Nature* 2016; 540:S100.
4. Ananthakrishnan AN. Epidemiology and risk factors for IBD. *Nature Reviews Gastroenterology & Hepatology* 2015; 12:205.

This study aims to obtain a diet therapy that can simulate the effect of EEN treatment but has a higher degree of compliance after scientific evaluation of the dietary therapy program CD-C-FOOD, so as to provide more effective approaches for CD treatment and improve the quality of life of patients to a large extent.

Key scientific problems to be solved:

1. To reveal the influence of CD-C-food on the inflammatory response and clinical treatment effect of patients with CD through intestinal microorganisms and metabolites, as well as its internal mechanism, which can be studied by 16S rRNA sequencing mass spectrometry for metabolite detection and pathological observation of animal models

2. To evaluate whether the therapeutic effect of CD-C-food on CD can achieve clinical remission effect. In the clinical pilot trial and subsequent large-sample verification of patients with CD, the study was conducted through observation of clinical inflammatory markers and comprehensive evaluation of clinical effect.

3. To reveal the effective mechanism of CD-C-FOOD and EEN, to conduct in-depth analysis of the process test products of the experimental group, and to conduct specific studies by using 16S rRNA sequencing mass spectrometry and pathological observation of animal models.

4. To evaluate whether the therapeutic effect of CD-C-food on CD can achieve clinical remission effect. In the clinical pilot trial and subsequent large-sample verification of patients with CD, the study was conducted through observation of clinical inflammatory markers and comprehensive evaluation of clinical effect.

3. Research protocol

1. Randomized controlled trials of healthy adults

(1) Specimen collection

A. Inclusion criteria:

- a. 30 healthy adults over the age of 18;
- b. Excluded subjects with any acute or chronic medical conditions (i.e., conditions requiring regular medical attention);
- c. In the past month weight stable (plus or minus 2 kg);
- d. There is no history of intestinal surgery;

e. No antibiotics or steroids have been used in the past 3 months.

B. Research procedure:

- a. The participants were randomly divided into two groups, group 1 and group 2 with 15 people in each group. During the experiment, dietary diary was recorded;
- b. During the first week, participants followed their usual eating habits;
- c. In the second week, group 1 received EEN and group 2 received CD-C-food for 7 days. In the CD-C-food group, participants were first tested for blood FOOD intolerance IgG4 assay. The participants were given half a dose of enteral nutrient solution and were presented with a list of foods to choose from which they preferred, excluding intolerant foods and excluding wheat bran, lactose, alcohol, food additives and any worker's ingredients. Personalized meal plans provided by research nutritionists provide their daily energy needs. Energy needs were calculated from participants' estimated basal metabolic rate and self-reported levels of physical activity. EEN and CD-C-FOOD meals were provided free of charge to participants along with written preparation instructions.
- d. The third and fourth week was a cleanup period, during which participants ate their usual diet and restored their gut microbiome to baseline, avoiding interference with contamination bias. In the third week, they followed their usual eating habits, and in the fourth week, they followed the diet of the first week and monitored their weight.
- e. In the fifth week, the diet of the second week was repeated, but the diets of the two groups were switched, with group 1 receiving CD-C-Food and group 2 receiving EEN, for a total of 7 days
- f. Appetite, gastrointestinal symptoms, and adherence to the experimental diet were assessed by questionnaire, and food adherence was further assessed by food surplus and food diary.

C. Sampling time: Fresh stool samples were collected at the end of the first, second, fourth, and fifth weeks. A total of four samples were provided by each participant.

(2) Detection of routine fecal indexes and study of intestinal microorganism:

- A.** The fresh Stool uses the Bristol Stool Form Scale to evaluate the shape and texture of the sample, and to measure the Stool water content, pH, and ammonia content.
- B.** Fecal microorganism detection: microbial diversity detection (16S rRNA second-generation sequencing) and quantitative microflora detection (qPCR quantitative detection).

(3) Detection of fecal bacterial metabolites

(4) Fecal metabolome study. Nontargeted metabolites of chloroform, methanol, and water (1:3:1) extracts were determined by high performance liquid chromatography-mass spectrometry (HPLC-MS).

2. Open label trial for CD patients

(1) specimen collection

A. Inclusion criteria:

- a. 200 patients with CD recurrence aged 6-15 years;
- b. Patients who had taken antibiotics within a month were excluded;
- c. Patients who changed CD treatment strategy within 1 to 3 months were excluded;
- d. The severity of the patient's illness required hospitalization;
- e. Exclude patients with FOOD allergies from CD-C-Food.

B. Research procedure:

- a. Participants were treated with CD-C-Food for 8 weeks. The FOOD supply was provided during the study period. The FOOD provided to CD patients was different from that of healthy volunteers, whose FOOD was directly packaged. Participants were asked to record their daily intake of food and drink.
- b. Clinical examinations were conducted at two-week intervals, and no changes to the drug associated with CD therapy were allowed during the trial. If disease activity deteriorates at any time, or does not improve by 4 weeks, the patient discontinues the CD-C-Food treatment. Patients who responded clinically but did not enter clinical remission after 8 weeks had the option to continue CD-C-food treatment for 4 weeks.
- c. Clinical response and clinical response were assessed every two weeks. Feces and blood were collected once at baseline, once after 4 weeks, again after 8 weeks, and again if a patient had completed 12 weeks of treatment.
- d. The detailed procedures of intestinal microbiome study, bacterial metabolites and intestinal metabolomics of patients were referred to the previous experimental procedures.
- e. Patients were tested for inflammatory cytokines in blood cells at all stages: The expression of TNF- α , interleukin (IL)-6, IL-10, IL-1B and CXCL-1 in the samples were detected by Milliplex (Merck) liquid-phase suspension chip technology.

(2) Clinical scores and clinical indicators:

CDAI (Crohn's disease activity index) scores were performed every two weeks, feces collected every four

weeks were tested for fecal calprotectin, and blood was tested for serum albumin and C-reactive protein.

3. Animal experiment

(1) samples:

Adult (36-40 weeks of age) 12 Piebald Virol Glaxo (PVG) heterozygous HLA-B27 and 8 HLA-B7 transgenic rats were studied. B27 rats express the human major histocompatibility complex class I HLA-B27 gene and the related human β 2-microglobulin gene and develop inflammation in their gastrointestinal tract (including ileum). They do not cause intestinal inflammation in a sterile environment, and antibiotic treatment can reduce the severity of ileitis. This model has been widely used in the study of inflammatory bowel disease, including with EEN intervention. The intestinal microbiota of B27 showed a similar phenotype to that of Cd, including an increase in proteobacteria and a decrease in sclerocytes. B7 rats did not have intestinal inflammation and were used as a control. Rats were placed in separate cages and raised under specific non-pathogenic conditions. Weight is monitored.

(2) procedures:

B27 rats was divided into three groups, which were CD-C-FOOD group, EEN group and conventional diet control group. B7 was divided into two groups, EEN group and normal diet control group. The net effect of EEN on their gut microbiota was studied in the B7 group setting without inflammation. There were 2 male rats and 2 female rats in each group, and there was no difference in body weight between groups.

4. Data analysis

The general linear model, Box-Cox transform and Fisher pair test were used for comparison between groups. The bacterial community diversity index among each group can be analyzed by alpha-diversity index. Community richness index (Chao and Ace) and Community diversity index (Shannon and Simpson) were calculated. The similarity and difference of microorganisms in different groups can be analyzed by Unifrac based PCoA. The differences between the groups were analyzed using NMDS (Nonmetric Multidimensional Scaling). PCA(Principal Component Analysis) principal component analysis can be used for grouping analysis between groups. Dietary pathology scores and metabolite markers were analyzed using SPSS, and fecal metabolites were analyzed using PCA, Unifrac based PCOA analysis, and permutation multivariate analysis of variance (PERMANOVA). Pearson test was used for correlation analysis. However, in metabolomic analysis, Spearman rank correlation test was used to compensate for the unbalanced influence of outliers, and Benjamin-Hochberg correction method was used to perform multiple

tests.

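### CD drug changes are barred throughout the trial while the diet is withdrawn at worsening; no rescue route is written, and the plan does not say whether a stopped child leaves the trial or how that child is counted

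*Combined protocol and SAP*

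**What the plan says.** All references are to the combined protocol and SAP, section 3 (Research protocol), part 2 (Open label trial for CD patients), unless stated otherwise.

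- **Population** (inclusion criteria, item a): "200 patients with CD recurrence aged 6-15 years".
- **Treatment** (research procedure, item a): "Participants were treated with CD-C-Food for 8 weeks".
- **Drug rule** (item b): "no changes to the drug associated with CD therapy were allowed during the trial". No exception follows.
- **Diet stopping rule** (item b, next sentence): "If disease activity deteriorates at any time, or does not improve by 4 weeks, the patient discontinues the CD-C-Food treatment".
- **Follow-up** (item c): "Clinical response and clinical response were assessed every two weeks". One of the two terms was probably meant to be remission. Stool and blood are taken at baseline, "once after 4 weeks, again after 8 weeks, and again if a patient had completed 12 weeks of treatment".
- **Activity index** (clinical scores and clinical indicators): CDAI "scores were performed every two weeks".
- **Question to be answered** (section 2, key scientific problems): "To evaluate whether the therapeutic effect of CD-C-food on CD can achieve clinical remission effect".

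The CD patient part names no rescue treatment, drug escalation, switch to exclusive enteral nutrition or return to usual care. It does not say whether stopping the diet ends participation. The data analysis part (section 3, part 4) covers group comparisons and microbiome and metabolite methods. It has no rule for early stops or for drug changes.

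**The concern.** The two sentences in item b pull in different directions for the same child. One withdraws the study treatment because the disease is worsening or not improving. The other, read literally, forbids the usual next step, which is to adjust the CD drugs. The children affected are the ones doing badly, and they are 6 to 15 years old and already in relapse. An investigator who follows the text must decide, without guidance, whether the child is still in the trial. If so, escalation is a protocol deviation.

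There is also a consequence for the result. The plan asks whether the diet can bring about remission. The drug ban, together with the exclusion of patients whose treatment strategy changed recently, shows that this is meant to be judged with drugs held stable. A remission reached at week 8 after a drug change does not answer that question. A treatment failure who leaves and is not counted distorts the answer as well. Nothing in the plan handles either case.

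**Working it through.** No stated figure needs to be reproduced. The check is a reading of item b against items a and c, followed by subtraction.

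**1. Does the text keep a stopped child in the trial?** The ban is tied to the trial, while the stopping rule is tied only to the diet. Item c attaches no on-treatment condition to the week-4 and week-8 samples, but does attach one to the week-12 sample. The two-weekly CDAI is also unconditional. This suggests that the child stays. It does not settle the matter: the week-12 condition may be there only because the extension is optional, and item c may describe only children still on the diet.

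**2. Length of the gap.** Inputs: 8 weeks of treatment (item a); stop at worsening at any time or at week 4 (item b); visits every two weeks. If the child stays to week 8, gap = 8 − week of stop.

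| Stop | Child stays | Child leaves |
|---|---|---|
| Soon after baseline | almost 8 weeks | 0 |
| Week 2 | 8 − 2 = 6 weeks | 0 |
| Week 4 | 8 − 4 = 4 weeks | 0 |
| Week 6 | 8 − 6 = 2 weeks | 0 |

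The documents support a range of 0 to almost 8 weeks and no single figure.

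**3. How many children.** The share who stop is not given. If it is 10%, 20% or 30% of 200 (assumed), that is 20, 40 or 60 children. At 0 to almost 8 weeks each, the upper limits are just under 20 × 8 = 160, 40 × 8 = 320 and 60 × 8 = 480 patient-weeks. The lower limit is 0 in each case.

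**4. Direction of the effect on a week-8 remission rate.** This is illustration only, because the plan defines no such rate.

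- *The child stays and drugs are changed.* Let s be the share stopped and r the share of those who remit by week 8 (r = 10% to 40%, assumed). Crediting them to the diet adds s × r: 1 to 4 points at s = 10%, 2 to 8 at s = 20%, 3 to 12 at s = 30%.
- *The child leaves and is not counted.* Suppose 100 of 200 remit and the early stops do not (assumed). The rate among those remaining is 100/180 = 55.6%, 100/160 = 62.5% or 100/140 = 71.4% for s = 10%, 20% or 30%, against 100/200 = 50% in everyone who started.

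For scale, the 95% half-width at an assumed 50% rate with n = 200 is 1.96 × √(0.5 × 0.5/200) = 6.9 points. In these illustrations both routes push the rate upward.

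**The case against.** The strongest reply is that stopping the diet may simply end participation. As this part is written, every patient receives CD-C-Food, so a child off the diet has little left to do in the trial; the ban would lapse and usual care would resume. The sponsor may well intend this. The reply stands as far as it goes: a reader might infer that a stopped child is certainly held without a permitted drug change until week 8, and the text does not say so. But it does not say the opposite either, and under this reading the failure has no week-8 result and no counting rule.

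A reader might also infer that such a child is left untreated. The documents do not support that. Item b bars changes to CD drugs, not the drugs themselves, so background treatment continues, and leaving the trial for usual care is not excluded.

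Two further objections are fair. The safety problem needs the ban to be obeyed and the rescue bias needs it to be breached, so the two cannot both arise from the same period in the same child. And with no primary endpoint, remission rate, analysis set or CDAI cut-off defined, there is no stated rate whose bias could be measured. Both limit what can be claimed about size. Neither removes the ambiguity in item b.

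**Conclusion.** The point holds in a conditional form and should be fixed. An unqualified ban on CD drug changes stands next to a rule that takes the diet away from worsening children, with no rescue route and no statement of trial status after a stop. If the child stays, drugs may not be adjusted for up to almost 8 weeks (4 after a stop at week 4). If the child leaves, the gap is 0 and the failure goes unrecorded at week 8. The first reading fits the written schedule somewhat better, but the plan does not choose.

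The counting problem is secondary and arises on both readings. A reader might take the illustrative percentage points as an estimate of bias. They are not: the stop share, the remission share after rescue and the 50% base rate are all assumed, and the size of any bias cannot be derived from the documents.

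**What to change.** **Item b.** Replace the phrase *during the trial* with: *while the patient is on CD-C-Food; once CD-C-Food is stopped, treatment is at the treating physician's discretion.* This removes the conflict whether or not the child stays in follow-up. Also state whether stopped children continue the scheduled visits.

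**Data collection.** Record the date of any CD drug change.

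**Data analysis.** Add: *Any week-8 remission or response rate is reported in everyone who started CD-C-Food. Patients who stopped CD-C-Food or changed CD drugs before week 8 count as not in remission or response. Samples taken after a drug change are flagged, and results are shown with and without them.* The last sentence covers calprotectin, C-reactive protein, albumin, cytokine and stool results. The rule works with whatever CDAI cut-offs the sponsor sets.

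**Cost.** One phrase, a few sentences, one date field and one data flag. The counting rule needs no week-8 visit from a stopped child, so it adds no visits or samples on either reading. Following stopped children for laboratory results would add visits only if the sponsor had meant them to leave. The price is a more conservative rate: a child who stopped the diet and recovered on other treatment counts as a failure of the diet.

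### Does the lack of a written rule for counting patients taken off CD-C-Food require a change to the plan?

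*Combined protocol and SAP*

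**What the plan says.** The relevant text is in section 3 (Research protocol), part 2 (Open label trial for CD patients), and in part 4 (Data analysis).

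- Treatment (Research procedure, item a): "Participants were treated with CD-C-Food for 8 weeks".
- Stopping (item b): "If disease activity deteriorates at any time, or does not improve by 4 weeks, the patient discontinues the CD-C-Food treatment".
- Extension (item b): "Patients who responded clinically but did not enter clinical remission after 8 weeks had the option to continue CD-C-food treatment for 4 weeks".
- Sampling (item c): stool and blood at baseline and week 4, "again after 8 weeks, and again if a patient had completed 12 weeks of treatment". Only the week-12 sample depends on having stayed on treatment.
- Scoring (Clinical scores and clinical indicators): "CDAI (Crohn's disease activity index) scores were performed every two weeks".
- Size (Inclusion criteria, item a): 200 patients aged 6 to 15 years. No other patient count appears for this part.

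Items 2 and 4 of the key scientific problems ask whether the diet achieves clinical remission. The Research background also has a sentence fragment on comparison with EEN: "By comparing the effects of this individualized diet with EEN on inducing and maintaining remission in CD patients". It quotes EEN remission rates of 67% in adults and 80% in Europe.

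The Data analysis section lists group tests, diversity indices, ordination, correlation and a multiplicity correction. It gives no primary endpoint, remission definition, analysis population or missing-data rule, and it does not say how a patient who stopped the diet is counted.

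**The concern.** Stopping is not random dropout. The protocol takes patients off the diet because an early reading of disease activity is poor, and disease activity is also what remission would be judged on. A week-8 rate among patients still on the diet would therefore come from a group already selected for doing well, and it would rise even if the diet did nothing. The patient part describes a single diet, so no parallel group shares the selection.

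Because the denominator is not written down, it could in principle be chosen after the results are known. At stake would be how close CD-C-Food appears to come to EEN, for which the documents give only the two background figures. Pooling week-12 results from the extension would be a further way to raise the rate, since only responders not yet in remission may continue.

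**Working it through.** **Nothing to reproduce.** The 200 comes with no power calculation, expected remission rate or dropout allowance, and no share stopped is given. Every input below except 200 is assumed.

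**Step 1: the simple ratio.** Let R be the number in remission on the diet, S the number stopped and N = 200, with s = S/N. If stopped patients count as not in remission, the all-enrolled rate is R/N and the on-diet rate is R/(N - S). Their ratio is N/(N - S) = 1/(1 - s), whatever R is. With R = 60 (assumed), the all-enrolled rate is 60/200 = 30.0% (Wilson 95% interval 24.1% to 36.7%).

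| Stopped | On-diet rate | Ratio |
|---|---|---|
| 10% | 60/180 = 33.3% | 1.11 |
| 30% | 60/140 = 42.9% | 1.43 |
| 50% | 60/100 = 60.0% | 2.00 |

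**Step 2: how much of that ratio is selection.** The ratio takes as its reference a rule under which nobody who stops can be in remission. That reference is itself low if some stopped patients are in remission at week 8. To separate the two effects, assume no diet effect, 30% of all patients in remission at week 8 by actual status, and a bivariate normal model with correlation 0.3 between week-4 and week-8 activity. The worst s at week 4 stop.

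| Stopped | On-diet rate | Stopped = not in remission | On-diet / true 30% | True 30% / composite |
|---|---|---|---|---|
| 10% | 31.8% | 28.6% | 1.06 | 1.05 |
| 30% | 35.0% | 24.5% | 1.17 | 1.22 |
| 50% | 38.4% | 19.2% | 1.28 | 1.56 |

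The last two columns multiply back to the simple ratio. At 30% stopped, 1.17 × 1.22 = 1.43; at 50%, 1.28 × 1.56 = 2.00. At this correlation, selection is the smaller part of the ratio at 30% and 50% stopped.

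In percentage points, selection adds 1.8, 5.0 and 8.4. The Wilson half-width at 60/200 is (36.7 - 24.1)/2 = 6.3 points. The first two shifts are below it and the third is above.

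**Step 3: sensitivity to the correlation.** At 30% stopped, the on-diet rate is 31.7%, 35.0%, 38.1% or 41.0% at correlations of 0.1, 0.3, 0.5 or 0.7. At 50% stopped it is 32.8%, 38.4%, 44.3% or 50.8%. So the effect can be large, but only if many patients stop, early activity strongly predicts week 8, and the analyst also restricts to on-diet patients.

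**Step 4: does the plan point to an on-diet analysis?** Setting the passages side by side: the only count is 200, the fortnightly CDAI and the week-8 samples are not limited to patients still on the diet, and the Data analysis section restricts nothing. The plan does not say outright that assessment continues after stopping, but it does attach a treatment condition to week 12 and none to week 8.

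**Step 5: continuous markers.** A simulation in which week-8 markers are missing after stopping (30% or 50% stopped) gave bias of -0.15 or -0.24 SD in retained patients. A marker-only likelihood model gave -0.08 or -0.13 SD. Those figures need a correlation of 0.3 between week-4 CDAI and the week-8 marker. At 0.15 the retained-only bias is -0.07 or -0.12 SD and the marker-only model has none. The documents give no value, so this does not support a demand for a particular model.

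**The case for a change.** The strongest case for a change is that the gap is certain, the trigger for stopping is an early reading of the outcome, and the trial is open label with one diet. A few sentences would close off a choice made after seeing the results, with no new visits. Under either all-enrolled rule a reader knows what was measured; under the present text the reader must wait for the report.

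Much of this stands. The rule is absent, the arithmetic in step 1 is exact under its stated convention, and an on-diet rate presented as the remission rate would mislead.

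Three parts do not carry through. First, the harm needs an analysis the plan does not propose. Second, the 67% and 80% figures are background: one is for adults while this part enrols ages 6 to 15, neither comes with a denominator, and no test against them is planned. Converting an on-diet 67% at 30% stopped into 0.67 × 0.70 = 46.9% of all enrolled therefore assumes a comparison that is not set up. Third, the remedy would pick one of two legitimate rules. Counting stopped patients as not in remission measures success on the diet; counting them by actual week-8 status measures the outcome of starting it. Each has a cost, and the documents do not make one of them wrong. Barring week-12 pooling would forbid something the plan never suggests.

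**Conclusion.** No change to the plan follows. This is missing detail that a competent analyst fills sensibly: report remission over the 200 enrolled, say how stopped patients were counted, and label any on-diet figure as descriptive. The choice between the two all-enrolled rules is a fair trade-off.

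If an on-diet rate were used after all, the inflation due to selection would be about 1.06, 1.17 or 1.28 times at 10%, 30% or 50% stopped, not 1.11, 1.43 or 2.00. That rests on an assumed 30% remission rate, no diet effect and a correlation of 0.3; a higher correlation raises it, and few stops make it small. The true share stopped is unknown. The conclusion also rests on reading the week-8 assessments as applying to everyone, which the wording supports but does not state. It makes no judgement on the stopping rule itself.
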